4 STUDY OBJECTIVES AND ENDPOINTS

4.1 Primary Objectives

- Evaluate DLTs, safety and tolerability of escalating dose levels of PF-07901801 when administered in combination with 40 mg/m² PLD in 28-day cycles and establish the MTD and RP2D combination regimen (Phase 1 portion of study)
- Assess preliminary evidence of anti-tumor activity of PF-07901801 in combination with 40 mg/m² PLD (Phase 2 portion of study)

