participant's disease. Exploratory endpoints include but are not limited to PK and immunogenicity of PF-07901801, PK of PLD, CA-125 levels, measurements of biomarkers/pharmacodynamics, which may consist of DNA, RNA, protein or defined cell types, resulting from analyses of peripheral blood and/or tumor tissue biospecimen obtained at baseline, on treatment and/or at end of study, as well as the single and multiple dose pharmacokinetics of PF-07901801.

PLD will be administered at 40 mg/m² on Day 1 of each 28-day cycle.

PF-07901801 will be administered by intravenous infusion; the duration of infusion is dependent on dose level with dose levels less than or equal to 33 mg/kg infused over 60 min and doses greater than 33 mg/kg infused over 90 minutes and will have doses equal to or less than 2500 mg in 250 mL and doses 2501 mg or more in 500 mL or neat drug if the drug volume is over 500 mL. Medications to treat infusion-related reactions and CPR equipment must be available for immediate use prior to initiation of PLD infusion.

The dose-limiting toxicity evaluation period will consist of the 28-day Cycle 1 or until participants experience a DLT in Cycle 1. Participants will be considered DLT evaluable if they receive PLD on Day 1 and at least two infusions of PF-07901801 in the 28-day Cycle 1. A participant who withdraws from the study during Cycle 1 in the absence of DLT evaluable (ie, not receiving PLD and at least two doses of PF-07901801) will be replaced. If a dose-limiting toxicity as defined in Section 5.4 is encountered in one participant in the initial three participants in a dose cohort, three additional participants will be enrolled in accordance with the standard 3+3 study design. The maximum tolerated dose (MTD) for this study will be defined as the highest PF-07901801 dose level at which <33% of participants within a dose cohort experience dose-limiting toxicity when administered in combination with PLD at 40 mg/m². While three pre-defined PF-07901801 dose levels are anticipated, intermediate dose levels may be studied to more closely characterize the safety profile of PF-07901801 in combination with PLD.

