After three to six participants in a dose cohort complete the 28-day dose-limiting toxicity assessment period, the incidence of dose-limiting toxicity, treatment-related safety observations and other available data, such as pharmacokinetic data, will be reviewed by the medical monitor, sponsor and investigators. If no participant in a three-participant cohort or no more than one participant in a six-participant dose cohort experiences treatment-related dose-limiting toxicity, the dose level will be deemed safe and dose escalation may proceed unless there are other unsuspected but concerning safety observations that suggest either an expansion of the current dose level or implementation of an intermediate dose level.

Objective disease assessments will be performed after every 8 ± 1 weeks through week 48, or until participant has been on study for one year, and every 12 ± 2 weeks thereafter. Participants who withdraw from the study without objective evidence of disease progression will be followed until documentation of disease progression or initiation of another treatment. All participants will be followed in the Long-Term Follow-Up period for survival.

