5.2 Doses and Schedule of Administration of Investigational Agents

PLD will be administered on Day 1 of 28-day cycles.

In Cycle 1 for dose levels 1 (12 mg/kg) and 2 (24 mg/kg), PF-07901801 will be administered on Day 1, Day 8, Day 15 and Day 22 of a 28-day cycle. Beginning with Cycle 2, PF-07901801 will be administered on Day 1 and Day 15 only of each 28-day cycle.

For dose level 3 (48 mg/kg) PF-07901801 will be administered on Day 1 and 15 of a 28-day cycle starting from Cycle 1. Loading doses (Day 8 and Day 22) may be considered for Cycle 1 at the 48 mg/kg dose level if found to be safe and offer clinical benefit for participants. If Cycle 1 loading doses are implemented, all dosing and lab draw schedules for the 48 mg/kg dose will follow the schedules for dose levels 12 mg/kg and 24 mg/kg.

The following rules apply during dose escalation:

- Starting dose at dose level 1 is 12 mg/kg.
- At least 3 participants will be enrolled at each dose level. When all participants at a dose level complete DLT assessments, the study will escalate to the next dose level and another 3 participants will be recruited in this order until MTD/RP2D.
- If agreed upon by the investigators and Pfizer (eg, based on safety, incidence of DTL, PK and dose-exposure data from prior and current cohorts) that increasing the dose further may not yield additional benefit, the dose may stay at the current dose level, be de-escalated to any dose, or no future escalation may be made, even if the dose escalation rule indicates to escalate.
- The need for dose escalation to a specific dose beyond 48 mg/kg or deescalation to an intermediate dose level will be evaluated jointly by investigators and Pfizer based on cumulative clinical safety, PK, and preliminary efficacy data.

Table 11.	Participants	Dose-Grouping,	Dose Esc	calation Plan
-----------	---------------------	----------------	----------	---------------

Cohort #/Dose Level	Dose of PF-07901801 (Intravenous)	Dose of PLD (Intravenous)
1	12 mg/kg	40 mg/m ²
2	24 mg/kg	40 mg/m^2
3	48 mg/kg	40 mg/m^2

[•] Participants will be considered DLT evaluable if they receive PLD on Day 1 and at least two infusions of PF-07901801 in the 28-day Cycle 1

- Participants who complete the DLT assessment window will be allowed to continue treatment until disease progression, intolerable toxicity, withdrawal of consent, lost to follow-up, end of study, or death, whichever comes first.

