12 STATISTICAL CONSIDERATIONS

12.1 Sample Size

12.1.1 Dose Escalation

The number of participants will depend on the number of dose cohorts that will be enrolled before reaching the MTD. It is anticipated that the study will evaluate three dose levels of PF-07901801 given in combination with a fixed dose of PLD. On the basis of emerging safety and/or clinical activity data, additional dose levels may be added. The size and design of the Phase 1 dose escalation phase of the study is consistent with standard 3+3 design with the objective of determining the safety of escalating doses of PF-07901801 in combination with fixed-dose PLD and establishing PF-07901801 doses for further evaluation in the intended participant population. Based on a standard 3+3 design, up to approximately six DLT-evaluable participants may be enrolled in each dose level cohort during the Phase 1 dose escalation portion of the study; a minimum of nine and a maximum of 18 DLT-evaluable participants is anticipated.

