12.1.2 Expansion Cohort

Phase 2 expansion cohort is planned to evaluate a selected PF-07901801 dose level in combination with a fixed dose of PLD. In this hypothesis-generating study, assuming an objective response rate of 10% with PLD monotherapy and an alternative of 30%, a power of 80% and one-sided Type 1 error set at 0.05, the combination will be considered worthy of further study if at least six responses are observed in the 25-participant cohort. If the dose level combination selected for further Phase 2 is determined to be not optimal or not well tolerated, an intermediate dose level, not to exceed the dose levels evaluated in Phase 1, may be implemented.

Other secondary endpoints, such as disease control, duration of response, progression-free survival and overall survival will be analyzed descriptively.

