13.12 Overview of Safety Monitoring

Throughout the study, investigators, site staff and the study sponsor will meet regularly to review the status of all active participants on study. During the dose escalation portion of the study, a regularly scheduled safety and information call will be held with participating investigators and site staff to discuss safety, review any questions, provide updates and to share information across sites. At the completion of each dose escalation cohort, safety data will be summarized and presented for discussion with all investigators for the purpose of determining whether the observed safety in each cohort warrants escalation to the next higher dose level or whether an alternate dose level or other action should be considered.

During the dose expansion portion of the study, these regularly-scheduled safety and information calls will continue; the calls will initially be held regularly although *ad hoc* meetings may be held as necessary to review specific safety or other issues that might arise during the course of the study. As the study progresses, the frequency of these safety and information calls may be adjusted to reflect need on the basis of safety observations observed, the rate of enrollment and investigator or sponsor request or need.

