4. STUDY DESIGN

4.1.Design Overview

This is a multi-center, open-label study designed to evaluate Maplirpacept (PF-07901801) administered in combination with PLD in participants with platinum-resistant recurrent epithelial ovarian cancer (EOC), including ovarian, peritoneal and fallopian tube malignancy, and for whom PLD is a reasonable treatment option. The study will consist of a 28-day screening period, a treatment period in which participants will receive PF-07901801 in combination with PLD in 28-day cycles until documentation of objective disease progression or development of unacceptable toxicity, and a long-term follow-up period to assess overall survival.

In the phase 1 dose escalation portion of the study, the primary objective is to assess DLTs, safety and tolerability of escalating dose levels of PF-07901801 in combination with PLD at the standard dose of 40 mg/m². Up to approximately 18 participants are planned to be enrolled in this portion of the study to evaluate three dose levels of PF-07901801 12 mg/kg (Dose Level 1), 24 mg/kg (Dose Level 2) and 48 mg/kg (Dose Level 3). In Cycle 1 for dose levels 1 and 2, PF-07901801 will be administered on Day 1, Day 8, Day 15, and Day 22 in combination with PLD on Day 1 of 28-day cycle. Beginning with Cycle 2 at dose levels 1 and 2, PF-07901801 will be administered on Day 1 and Day 15 in combination with PLD on Day 1 of 28-day cycles. The enhanced dosing in Cycle 1 represents a loading cycle and is intended to allow PF-07901801 levels to reach steady state more quickly. For dose level 3, PF-07901801 will be administered on Day 1 and Day 15 in combination with PLD on Day 1 of 28-day cycles. Loading doses (Day 8 and Day 22) may be considered for Cycle 1 at the 48 mg/kg dose (Dose Level 3) if found to be safe and offer clinical benefit for participants. If Cycle 1 loading doses are implemented, all dosing and lab draw schedules for the 48 mg/kg dose will follow the schedules for dose levels 12 mg/kg and 24 mg/kg.

One dose level combination will be selected for further evaluation in the phase 2 expansion portion of the study. The primary objective of the phase 2 expansion portion of the study is investigation of clinical activity of the combination of PLD and PF-07901801, assessed using the overall response by RECIST v1.1.

Template No.: NVA_TP_CR694 Revision 4 Reference: SOPCR008, WPCR013 Template Effective Date:15Feb2023

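### Cycle 1 loading at 48 mg/kg doubles the planned Cycle 1 dose, yet the plan as written lets it start on DLT data from the unloaded schedule

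*Protocol*

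**What the plan says.** **Schedule.** Under Protocol 5.2, 12 and 24 mg/kg are infused on Days 1, 8, 15 and 22 of Cycle 1, and 48 mg/kg on Days 1 and 15 only. The same section then says "Loading doses (Day 8 and Day 22) may be considered for Cycle 1 at the 48 mg/kg dose level if found to be safe" and beneficial. SAP 4.1 repeats this, placing it inside the existing level: loading "may be considered for Cycle 1 at the 48 mg/kg dose (Dose Level 3) if found to be safe and offer clinical benefit". Neither document says who decides, on what data, or in how many participants.

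**Clearance rules.** Protocol 5.1 defines the MTD as the "highest PF-07901801 dose level at which <33% of participants within a dose cohort experience dose-limiting toxicity". A level passes with no DLT in three participants, or if "no more than one participant in a six-participant dose cohort experiences treatment-related dose-limiting toxicity". Table 11 identifies cohorts by mg/kg alone. Protocol 12.1.2 caps any intermediate Phase 2 dose as "not to exceed the dose levels evaluated in Phase 1". Protocol 13.12 has investigators review each completed cohort for the purpose of "determining whether the observed safety in each cohort warrants escalation to the next higher dose level".

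**DLT population.** Protocol 12.2 and SAP 5.6.2 restrict it to Phase 1. A participant without a DLT needs PLD, two PF-07901801 infusions and completed Cycle 1 safety evaluations, whatever the schedule.

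**Exposure and response.** For DL3, SAP 8.1 fixes planned dose at 48 × C × 2 and always adds 14 days to the dosing interval for duration. SAP 7.1.1 provides a combined Phase 1 and Phase 2 response rate at the common dose and does not mention schedule.

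**The concern.** DLTs are counted only in Cycle 1, which is also the only cycle in which the loaded and unloaded 48 mg/kg schedules differ. A clean DLT result on two infusions therefore says nothing direct about four. Because clearance attaches to the mg/kg level, a team could read the safety condition for loading as met once unloaded 48 mg/kg has passed, with no participant having completed a loaded Cycle 1.

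Nothing readable confines loading to Phase 1. Protocol Table 32 covers sampling in an expansion at 48 mg/kg and carries the loading footnote. Loading first used there would have safety calls and general monitoring but no formal DLT analysis.

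In the SAP, loaded participants would be measured against a two-infusion plan, and the combined response rate could mix two Cycle 1 schedules under one dose label.

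**Working it through.** **1. Planned Cycle 1 dose** (dose per infusion × planned infusions, Protocol 5.2). The SAP's own DL3 formula at C = 1 gives 48 × 1 × 2 = 96 mg/kg, which agrees with the protocol schedule.

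| Schedule | Calculation | Cycle 1 total |
|---|---|---|
| DL1 | 12 × 4 | 48 mg/kg |
| DL2 | 24 × 4 | 96 mg/kg |
| DL3, unloaded | 48 × 2 | 96 mg/kg |
| 48 mg/kg, loaded | 48 × 4 | 192 mg/kg |

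The loaded total is 192/96 = 2 times the highest other total and 192/48 = 4 times DL1. The escalation plan tests 24 mg/kg weekly and 48 mg/kg every two weeks, but not 48 mg/kg weekly.

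**2. Unit of each rule.** The 3+3 expansion, the pass rule, the MTD and the minimum of three participants (Protocol 5.1, 5.2, 7.2) use the dose level or dose cohort. The Phase 2 cap (12.1.2) uses the dose level. None uses dose plus schedule, so adding Days 8 and 22 at 48 mg/kg triggers no new count.

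**3. Evaluability.** Two infusions at 48 mg/kg is 96 mg/kg, the full unloaded exposure. Even in a cohort assigned to loading, a DLT-free participant who received two of four infusions would count. Three infusions give 48 × 3 = 144 mg/kg. Only Days 1 and 15 are non-loading days, so three infusions must include at least one on Day 8 or Day 22.

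**4. SAP 8.1 for a fully dosed loaded participant.** Received = 192 + 96(C − 1); planned by the DL3 formula = 96C.
- C = 1: 192/96 = 200%
- C = 2: 288/192 = 150%
- C = 4: 480/384 = 125%

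These use the opening definition in SAP 8.1, received over planned. The later printed line for PF-07901801 intensity divides planned dose by PLD received; that is a separate error and is not used here.

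For duration, if the last dose is Cycle 1 Day 22, the DL3 rule gives (21 + 14)/7 = 5 weeks and the DL1/DL2 Cycle 1 rule gives (21 + 7)/7 = 4 weeks.

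**5. Risk that a separate 3+3 stops an acceptable loaded schedule.** With true DLT rate p and q = 1 − p, P(pass) = q³ + 3pq² × q³. The rates are assumed; the documents give none.
- p = 0.10: 0.729 + 0.177 = 0.906, so 9% are stopped.
- p = 0.20: 0.512 + 0.197 = 0.709, so 29% are stopped.

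**The case against.** Several provisions point towards care with loading.
- Safety is a stated condition, and the natural benchmark is the protocol's own pass rule.
- Protocol 4.1 asks Phase 1 to establish a combination regimen, and 3.4 speaks of a recommended Phase 2 regimen. A regimen includes its schedule, so first use of loading in expansion fits that wording poorly.
- Any Phase 1 participant who is loaded falls inside the DLT window.
- The re-treatment criteria in 9.1.2 apply on every dosing day, and blood tests are already scheduled on Cycle 1 Days 8 and 22.
- Under 12.1.1, "additional dose levels may be added", so a separate cohort is available.
- The stated default for Level 3 is two-weekly dosing from the start (3.7.1).

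All of this stands, and it lowers the severity. It makes a loaded DLT assessment possible and sensible; none of it requires one.

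On the SAP side, the DL3 schedule cell in 8.1 carries a footnote whose text is unreadable and may address loading, and SAP 1.1 allows changes before database lock. A synopsis figure is also missing, and the DLT criteria in Protocol 5.4 are redacted, although that section is introduced as a list of DLT events. The SAP part is therefore conditional on the footnote.

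A reader might also take the chance of failing a 3+3 at high DLT rates as a measure of the harm avoided. That is generic 3+3 behaviour at assumed rates. It is not conditioned on unloaded 48 mg/kg having passed, and the documents give no dose-toxicity data to link to it.

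**Conclusion.** The concern holds as a minor design gap. Loading doubles the planned Cycle 1 dose, from 96 to 192 mg/kg, and the readable rules allow that step on DLT data gathered at half the exposure, including for the first time in expansion. If loading is used, the readable DL3 planned-dose formula also gives full dosing as 200% of plan after one cycle, 150% after two and 125% after four.

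Two further inferences are not supported. The documents do not show that the loaded schedule is unsafe, or that the team intends to skip a DLT assessment; they only fail to require one. Nor is the Phase 2 decision compromised: the rule of six responses in 25 does not depend on this, and the by-phase displays stay separate. Only the descriptive combined response rate could mix schedules.

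The conclusion assumes that the unreadable footnote, the missing figure and the redacted text contain no rule for loading. It matters only if loading is adopted.

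**What to change.** **Protocol 5.1/5.2.** State that 48 mg/kg with Cycle 1 loading is a separate dose cohort. Assess its first three to six participants under the existing 3+3 and <33% rules, without pooling them with unloaded participants, before wider use. In that cohort, a participant without a DLT counts as evaluable only with at least three Cycle 1 infusions, so at least one loading infusion.

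**SAP 8.1.** For loaded 48 mg/kg participants, set planned dose to (48 × 4) + (48 × [C − 1] × 2) and use the DL1/DL2 duration rule, unless the unreadable footnote already does so.

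**SAP 7.1.1.** Show the combined response rate at the common dose by Cycle 1 schedule.

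**Cost.** One or two protocol sentences and a few SAP lines. Only if loading is used:
- up to three to six more DLT-evaluable participants, and one more 28-day window per group of three;
- smaller groups in the combined response display;
- a 9% chance of stopping a loaded schedule whose true DLT rate is 10%, or 29% at 20% (assumed rates).

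The maximum would rise from 18 + 30 = 48 to 24 + 30 = 54, against a planned total of about 50, or 24 + 25 = 49 with a 25-participant expansion. This takes no view on which schedule should be used.

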7.2 Method of Assigning Subjects to Treatment Groups

The dose escalation portion of the study carries a traditional 3+3 design to evaluate three dose levels of PF-07901801 in combination with fixed-dose PLD (40 mg/m²). Standard guidelines for enrollment for the 3+3 design will be followed, with requirement that three participants complete the 28-day safety assessment period before the next dose cohort is open to enrollment and expansion to six participants in the case of a treatment-related dose-limiting toxicity.

Only a single PF-07901801 dose level in combination with fixed-dose PLD (40 mg/m²) is planned for evaluation in the dose expansion portion of the study. During the dose expansion portion of the study, eligible participants will be enrolled into this cohort in chronological order of eligibility verification as they complete screening assessments.

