8. SAFETY ANALYSES

Summary of AEs and other safety parameters will be based on the safety analysis set (SAS) by phase and dose cohort, except for the DLT, which will be based on DLT-Evaluable Population (DLP) by dose cohort.

8.1.Exposure

On Day 1 of each cycle, PLD will precede administration of PF-07901801. An observation period between completion of PLD infusion and initiation of PF-07901801 infusion is not mandated. Cohorts/dose levels for phase 1 escalation

Template No.: NVA_TP_CR694 Revision 4 Reference: SOPCR008, WPCR013 Template Effective Date:15Feb2023 Page 25 of 46

Pfizer Inc. / Protocol: C4971002 (TTI-622-02) IQVIA Biotech (Confidential) Project # ZZA82397

part of the study with the intravenous exposure to study drugs PLD and PF-07901801 (after PLD) and its schedule of administration per 28-day cycle is summarized below:

Cohort / Dose Level (DL)	PLD Dose [mg/m²] Schedule of administration	PF-07901801 Dose [mg/kg] Schedule of administration
1	40 Day 1 of every 28 day-cycle	12 Cycle 1: Day 1, Day 8, Day 15, and Day 22 Cycle 2 and above: Day 1 and Day 15
2	40 Day 1 of every 28 day-cycle	24 Cycle 1: Day 1, Day 8, Day 15, and Day 22 Cycle 2 and above: Day 1 and Day 15
3	40 Day 1 of every 28 day-cycle	48 Any cycle: Day 1 and Day 15 ^a

The following rules apply during dose escalation:

- Starting dose at dose level 1 is 12 mg/kg.
- At least 3 participants will be enrolled at each dose level. When all participants at a dose level
 complete DLT assessments, the study will escalate to the next dose level and another 3 participants
 will be recruited in this order until MTD/RP2D.
- If agreed upon by the investigators and Pfizer (eg, based on safety, incidence of DLT, PK and dose-exposure data from prior and current cohorts) that increasing the dose further may not yield additional benefit, the dose may stay at the current dose level, be de-escalated to any dose, or no future escalation may be made, even if the dose escalation rule indicates to escalate.
- The need for dose escalation to a specific dose beyond 48 mg/kg or de-escalation to an intermediate
 dose level will be evaluated jointly by investigators and Pfizer based on cumulative clinical safety,
 PK, and preliminary efficacy data.

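### The escalation bullet in Protocol 5.2, repeated in SAP 8.1, gives no DLT condition or expansion step and so conflicts with the 3+3 rule in the synopsis, 5.1 and 7.2

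*Protocol*

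**What the plan says.** **Protocol 5.2** opens its list with "The following rules apply during dose escalation". The bullet at issue asks for at least three participants per level and continues: "When all participants at a dose level complete DLT assessments, the study will escalate to the next dose level". It ends: "another 3 participants will be recruited in this order until MTD/RP2D". No DLT count appears in it. The following bullet lets investigators and sponsor agree, on grounds that include DLT incidence, "that increasing the dose further may not yield additional benefit, the dose may stay at the current dose level"; they may also de-escalate or stop escalating.

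**SAP 8.1 (Exposure)** carries the same bullet: "complete DLT assessments, the study will escalate to the next dose level and another 3 participants".

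**Protocol 5.1**, matched by the synopsis, sends one DLT in the first three participants to three more at the same level. Its condition for going up is: "If no participant in a three-participant cohort or no more than one participant in a six-participant dose cohort experiences treatment-related dose-limiting toxicity". Even then escalation is permitted, not required, and follows review by the medical monitor, sponsor and investigators. The same section defines the MTD as the highest level with a DLT proportion below 33%.

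**Protocol 7.2** requires three participants to finish the 28-day window before the next cohort opens, and calls for "expansion to six participants in the case of a treatment-related dose-limiting toxicity".

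**SAP 4.2** names the 3+3 design, with about six DLT-evaluable participants at most per level. The 0/3 and 1/6 counts appear neither there nor in SAP 4.1, 8.1 or 8.3.

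**The concern.** Evaluating DLTs and establishing the MTD and RP2D is the primary objective of Phase 1, and the step from one level to the next is its main safety decision. The list that presents itself as the operative rules makes completion of assessment the only stated trigger, whereas 5.1 and 7.2 make the DLT count the trigger. Once a DLT has occurred, someone working from 5.2 and someone working from 5.1 can reach different next steps from the same data. Someone working from the SAP alone finds 3+3 named, but the only escalation rule spelled out there is the one without counts.

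**Working it through.** **1. The plan's own figure.** Protocol 12.1.1 anticipates 9 to 18 DLT-evaluable participants over three levels. The minimum is 3 levels × 3 = 9 and the maximum is 3 levels × 6 = 18, so both reproduce. The 18 relies on the expansion step in 5.1 and 7.2. The 5.2 bullet does not exclude six at a level, since it says at least three, but it supplies no DLT-driven route to six.

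**2. The texts side by side.**

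| DLTs observed | Synopsis, 5.1, 7.2 | 5.2 bullet and SAP 8.1 |
|---|---|---|
| 0/3 | escalation permitted after review | escalate |
| 1/3 | add three at the same level | escalate, unless the MTD end point is read as a stop |
| 1/6 | escalation permitted after review | escalate |
| 2/3 or 3/3 | condition not met | escalate, unless the MTD end point is read as a stop |
| 2/6 or more | condition not met | escalate, unless the MTD end point is read as a stop |

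The MTD end point works only through the below-33% definition. Since 1/6 = 16.7%, that level qualifies. Since 1/3 = 2/6 = 33.3%, neither of those does. Applied at 1/3, the definition would point to stopping, which is a third action beside expanding and escalating. The end point therefore does not supply the missing expansion step.

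**3. How often the difference could arise.** The documents give no true DLT rate, so p is assumed over a range, with independent outcomes and six reached only by expansion after 1/3.

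- P(0/3) = (1 − p)³
- P(1/3) = 3p(1 − p)²
- P(5.1 condition met) = P(0/3) + P(1/3) × (1 − p)³
- P(any DLT in first three) = 1 − (1 − p)³

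| p | P(0/3) | P(1/3) | 5.1 condition met | Any DLT in first three |
|---|---|---|---|---|
| 0.10 | 0.729 | 0.243 | 0.906 | 0.271 |
| 0.20 | 0.512 | 0.384 | 0.709 | 0.488 |
| 0.30 | 0.343 | 0.441 | 0.494 | 0.657 |
| 0.40 | 0.216 | 0.432 | 0.309 | 0.784 |
| 0.50 | 0.125 | 0.375 | 0.172 | 0.875 |

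Worked at p = 0.30: 0.343 + 0.441 × 0.343 = 0.494.

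The clearest point of conflict, exactly 1/3, has probability 0.24 to 0.44 at a given level across this range. Some DLT occurs among the first three with probability 0.27 to 0.88.

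**The case against.** The strongest reply is that nobody reading the whole protocol would escalate blindly. The 3+3 design is named in the synopsis, 5.1, 7.2, 12.1.1 and within 5.2 itself, at 5.2.2. The bullet's wording leaves room for a cohort of six, and its end point bears on 2/3 and 3/3, because such a level cannot satisfy the MTD definition. The next bullet cites DLT incidence and refers to a dose escalation rule that it may override, which presupposes a rule such as the one in 5.1. Section 5.1 requires a review of DLT incidence, and 13.12 requires safety data to be discussed after each cohort to decide whether escalation is warranted. SAP 1.1 says that the SAP governs the final analysis; it does not govern dosing.

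Most of this stands, and it rules out a stronger inference that a reader might draw: that the plan orders escalation whatever the DLT count, so that every level would be cleared with certainty. That reading has to ignore the end point and both reviews. Nor do the documents support treating 5.2 as a deliberate competing design.

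The reply does not remove the gap. The end point is indirect and omits the expansion step. The override is discretionary and worded around lack of additional benefit. The reviews say who decides and on what data, but they do not reconcile the two triggers.

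**Conclusion.** The inconsistency is real and should be corrected. The 5.2 bullet and its SAP copy state no DLT condition for each step and no expansion, whereas the synopsis, 5.1 and 7.2 state both. The conflict is direct at 1/3. At 2/3 or 3/3 it is softened, because the end point gives an indirect stop. The likeliest explanation is a shortened restatement of the 3+3 rule.

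At assumed true DLT rates of 0.10 to 0.50, a level meets the 5.1 condition with probability 0.91 to 0.17, so the situations in which the texts part are not rare. Those probabilities depend on the assumed rates and measure the reach of the wording, not what sites would do. No planned analysis changes, and neither does the stated sample size.

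**What to change.** Reconcile the escalation text in the synopsis, Protocol 5.1, 5.2 and 7.2, and SAP 8.1, so that both documents state one and the same rule, covering what happens after each DLT count and how the MTD/RP2D end point enters. Which rule applies is for the sponsor and investigators to confirm; this review does not choose one. The cost is about one clause in Protocol 5.2 and one in SAP 8.1. If the confirmed rule keeps three to six DLT-evaluable participants at each of three levels, the range of 9 to 18 stands.
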